3.2.6.1.2. Adverse Event Duration

Duration of AEs will be the AE end date minus the AE start date + 1. Adverse event duration will be computed within each treatment session. Adverse events still ongoing at the end of the study or containing partial start or stop dates will not be included in the analysis of AE duration.

The duration of AEs will be used to determine the categories of AE durations (≥ 1 to ≤ 4 days, > 4 to ≤ 7 days, > 7 to ≤ 14 days, ≥ 15 to ≤ 21 days, and >21 days). For ongoing AEs, the category of AE duration will be missing unless those events have an onset date 21 days prior to the subject's last visit in the study. In this case, the category of the AE duration will be classified as " > 21 days".

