- Table by preferred term and treatment session – If an AE preferred term occurred multiple times with a body system for the same subject within a treatment session, the preferred term will only be counted once for the subject in the treatment session for the summary of preferred terms. If an AE preferred term occurred multiple times within a body system for the same subject in different treatment sessions, the preferred term will be counted at each treatment session. If an AE body system occurred multiple times for the same subject within a treatment session, the body system will only be counted once for the subject in the treatment session for the summary of body systems. If an AE body system occurred multiple times for the same subject in different treatment sessions, the body system will be counted at each treatment session for the summary of body systems. If a subject has any AE within a treatment session, the subject will be counted once in the treatment session in the summary of subjects with at least one AE. If a subject has any AE in different treatment sessions, the subject will be counted in each treatment session in the summary of subjects with at least one AE.
- Table by duration of treated-related TEAE and treatment session – For each subject within each treatment session, every event will have its duration calculated. The multiple events for the same SOC and the same PT will be combined together for the sum of duration. Therefore for each SOC/PT in each treatment session, each subject will only have at most one (sum) duration which will be classified into one of the duration categories (≥ 1 to ≤ 4 days, > 4 to ≤ 7 days, > 7 to ≤ 14 days, ≥ 15 to ≤ 21 days, and >21 days).
- For ongoing AEs, the category of AE duration will be missing unless those events have an onset date 21 days prior to the subject's last visit in the study. In this case, the category of the AE duration will be classified as " > 21 days".
- Table of frequency of preferred terms – Preferred terms will be ordered by their descending frequency in the overall safety population. If 2 or more preferred terms are tied in their frequency, then the preferred terms will be ordered alphabetically.

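### The SAP gives incompatible rules for adverse events still ongoing at study end: one sentence drops them from the duration analysis, while the category rule puts those with onset at least 21 days before the last visit in the >21-day band

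*SAP*

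**What the plan says.** SAP section 3.2.6.1.2 defines duration from dates: "Duration of AEs will be the AE end date minus the AE start date + 1". It then removes two kinds of event from the duration analysis: "Adverse events still ongoing at the end of the study or containing partial start or stop dates will not be included".

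The next paragraph of the same section sets up five duration bands, the last being >21 days, and gives a separate rule for ongoing events: "the category of AE duration will be missing unless those events have an onset date 21 days prior to the" subject's last visit. For events that meet the exception, the text continues "In this case, the category of the AE duration will be classified as" >21 days.

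SAP section 3.4.7.1.1 repeats this category rule among the table conventions and does not repeat the exclusion. It also says that events with the same system organ class and preferred term are summed within a treatment session, so that "each subject will only have at most one (sum) duration which will be classified into one of the duration categories".

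SAP section 3.5.2 specifies a dataset for the duration analysis and refers back to section 3.2.6.1.2. The dataset is to hold only subject number, treatment session, body system, preferred term and total duration.

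**The concern.** An ongoing AE with onset at least 21 days before the last visit is left out under one sentence and counted in the longest band under the next paragraph. Both cannot apply to the same table.

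The exclusion is not neutral. An event is removed because it had not ended, so in subjects who complete Day 180 it removes the longest-lasting events first. What remains would look more transient than the data show.

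Safety is the primary objective. Protocol section 8.1.3 describes most earlier treatment-emergent AEs as transient, and section 8.4 says that most AEs resolved before the next scheduled treatment, which is a 21-day interval. The >21-day band is the part of the planned output that bears most directly on that description.

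**Working it through.** The documents state no figure on this point, so there is nothing to reproduce. The check sets the rules side by side and then does the arithmetic.

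**1. Ongoing AEs under each rule**

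| Onset relative to last visit | Exclusion sentence (3.2.6.1.2) | Category rule (3.2.6.1.2 and 3.4.7.1.1) |
|---|---|---|
| At least 21 days before | left out | >21 days |
| Less than 21 days before | left out | missing |

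The rules conflict in the first row. In the second row neither gives the event a band. The first row reads the category rule as at least 21 days; the SAP literally says 21 days prior.

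**2. Is the >21 label correct?** With duration = end − start + 1, an event with onset exactly 21 days before the last visit has lasted at least 21 + 1 = 22 days. The label is right.

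**3. Which events does the exclusion drop?** Inputs: injections on Days 1, 22 and 43, the last two with a window of ±3 days, and end of study at Day 180 (SAP section 3.1 and Table 1). For a reaction that starts on an injection day and is ongoing at Day 180, the minimum duration is 180 − onset day + 1:

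- Day 1: 180 days
- Day 22: 159 days
- Day 43: 138 days
- Day 46 (window limit): 135 days

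With a last visit on Day 180, every ongoing AE with onset by Day 180 − 21 = Day 159 meets the >21-day exception.

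**4. Effect on the >21-day share.** Take the entries that the category rule can place in a band. Let f be the fraction ongoing with onset at least 21 days before the last visit, and r the fraction of resolved entries lasting >21 days. The documents give neither, so both are assumed over a range.

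- Exclusion followed: share = r
- Category rule followed: share = f + (1 − f)r
- Understatement: f + (1 − f)r − r = f(1 − r)

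For r = 20%: f = 5% gives 0.05 + 0.95 × 0.20 = 24.0%, and f = 10% gives 0.10 + 0.90 × 0.20 = 28.0%, against 20.0% under exclusion.

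Understatement in percentage points:

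| f | r = 5% | r = 20% | r = 40% |
|---|---|---|---|
| 1% | 1.0 | 0.8 | 0.6 |
| 2% | 1.9 | 1.6 | 1.2 |
| 5% | 4.8 | 4.0 | 3.0 |
| 10% | 9.5 | 8.0 | 6.0 |
| 20% | 19.0 | 16.0 | 12.0 |

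**5. A small-number example.** Protocol section 8.3 gives injection site nodule in 14.3% of treated women in the Phase 2b study. Used only for scale, 0.143 × 150 is about 21 subjects. Suppose 2 are ongoing and 4 resolved after more than 21 days (both assumed). Exclusion gives 4/19 = 21.1%; the category rule gives (4 + 2)/21 = 28.6%.

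**6. Mixed events.** Suppose one nodule resolves in 6 days and another, in the same subject and session, is ongoing. Section 3.4.7.1.1 sums durations within the preferred term, but no rule says how the ongoing event enters the sum. Adding only the available durations gives 6 days, which falls in the band above 4 and up to 7 days. This gap exists even if the category rule governs.

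**The case against.** The strongest reply is that section 3.2.6.1.2 describes two variables. Its first paragraph concerns numeric duration, which cannot be computed without an end date; its second concerns the category. Section 3.4.7.1.1, which governs the actual table, repeats only the category rule. Read that way, early-onset ongoing events stay in the >21-day band and nothing is biased. This reading is workable, so the bias is conditional.

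It does not remove the conflict. No sentence limits the exclusion to numeric summaries. The band table is the only duration output whose content the SAP text describes, so on this reading the exclusion would govern no described output. Section 3.5.2 sends the programmer back to the section that contains the exclusion, and the dataset as listed has no field for ongoing status or category. The table shells in SAP Module 2 might settle the matter, but they are not among the documents.

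Other parts of the reply stand:

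- Unresolved events are not hidden altogether. Ongoing status and outcome are collected (SAP section 3.1.9) and all AEs are listed (SAP section 3.4.7.1).
- Protocol section 14.5.1 follows ongoing AEs for up to 30 days after the last visit, so some will gain an end date.
- The analysis is descriptive and single-arm.

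A reader might also infer that earlier nodule, induration or mass rates show that such events persist to Day 180. They are incidences and say nothing about persistence.

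**Conclusion.** The conflict holds for AEs ongoing at study end with onset at least 21 days before the last visit. If the exclusion sentence prevails, the >21-day share is understated by f(1 − r): 4 points at f = 5% and 8 points at f = 10% when r = 20%. Those inputs are assumptions. The formula takes entries with a band as the denominator and treats each entry as either resolved or ongoing. If section 3.4.7.1.1 prevails, this bias is zero, though the mixed-event gap remains.

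Four stronger readings are not supported:

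- That the SAP classes all ongoing AEs as >21 days. Missing is the default and >21 days the exception, although the exception covers injection-day reactions ongoing in Day 180 completers.
- That the plan will shorten reported durations. That depends on which rule is applied.
- That a mean duration would be biased by some number of days. The SAP text specifies no mean AE duration.
- That events with a missing category disappear from the table. The text does not say how they are displayed.

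This is worth correcting because the rule as written can be followed in a biased way in a summary that serves the primary objective. It does not threaten the study's conclusions as a whole.

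**What to change.** 1. In section 3.2.6.1.2, delete the exclusion of ongoing AEs, or limit it explicitly to any numeric duration summary. State that the category table follows section 3.4.7.1.1.
2. In both sections, say that onset must be at least 21 days before the last visit.
3. Show ongoing AEs with shorter observed time, and AEs with partial dates, as separate rows kept in the denominator.
4. State that a subject, preferred term and session with any ongoing event is classed by its minimum elapsed duration, not by the resolved events alone.
5. Let the section 3.5.2 duration dataset carry an ongoing flag or the derived category.

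The cost is minor SAP and programming edits, with a duration table that may look slightly less favourable. A Kaplan-Meier analysis is not needed unless a continuous duration summary is produced.

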3.2.6.2. Vital Signs and Clinical Laboratories

3.2.6.2.1. Baseline Values and Change from Baseline Values

The baseline values for vital signs and clinical laboratories will be the last available measurement prior to the first dose of study medication. For clinical laboratories this could be the screening value or it could be an unscheduled lab, if the unscheduled lab is the closest value preceding the first injection. For vital signs, baseline will be Day 1 pre-dose for the by visit analyses.

Vital signs will additionally be analyzed on each injection day. For the first treatment session, baseline will be the last available measurement prior to the injection (Day 1 pre-dose). For Day 22 and Day 43, baseline will be the last available pre-injection measurement taken on that day.

Change from baseline will be the visit/time point value minus the baseline value.

3.2.6.2.2. Sponsor-Defined Potentially Clinically Important Vital Sign Values

Table 5 presents the criteria for determining potentially clinically important (PCI) vital sign values.

Table 5: Sponsor-Defined Potentially Clinically Important Vital Sign Criteria

Parameter	PCI Low	PCI High
Systolic blood pressure	≤ 90 mmHg and decrease ≥ 20 mmHg from baseline	≥ 180 mmHg and increase ≥ 20 mmHg from baseline
Diastolic blood pressure	≤ 50 mmHg and decrease ≥ 15 mmHg from baseline	≥ 105 mmHg and increase ≥ 15 mmHg from baseline
Pulse rate	≤ 50 bpm and decrease ≥ 15 bpm from baseline	≥ 120 bpm and increase ≥ 15 bpm from baseline
Respiratory rate	≤ 8 brpm and decrease ≥ 7 brpm from baseline	≥ 25 brpm and increase ≥ 7 brpm from baseline
Temperature		≥ 38.3°C and increase ≥ 1.1°C from baseline

3.2.6.2.3. Sponsor-Defined Potentially Clinically Important Laboratory Values

Table 6 presents the criteria for determining PCI laboratory values.

Table 6: Sponsor-Defined Potentially Clinically Important Laboratory Criteria

Analyte	PCI Low: Less than or equal to	PCI High: Greater than or equal to
Hemoglobin (g/L)	100	190
Hematocrit	0.3	0.6
Platelets (10 ⁹ /L)	100	650
ALT (U/L)		3xULN ^a
AST (U/L)		3xULN ^a
Creatinine (μmol/L)		300
BUN (mmol/L)		12

^a ULN=Upper limit of normal.

3.2.6.3. Immunogenicity

Seropositivity and titer levels for both anti-AUX-I and anti-AUX-II antibodies will be obtained from each analyzed sample. Samples with a positive titer value will undergo a log transformation for analyses. Samples that are less than 1 titer will be analyzed with a log transformed titer of 0.

A subset of samples from Day 1 and Day 180 (EOS/ET) will be analyzed for neutralizing antibodies.

3.2.6.4. Medical History

Medical history will be mapped to preferred term using MedDRA, Version 19.0. Subjects with medical histories of Dupuytren’s Disease, Ledderhose’s Disease, Knuckle Pads, Diabetes, and

Epilepsy will be summarized. Subjects will be coded as having these disorders based on the preferred term of their reported medical histories. Knuckle pads will also include the preferred term of ‘Garrod pads’. Ledderhose’s disease will also include the preferred term of ‘Fibromatosis’. Epilepsy will also include the preferred term of ‘Convulsion’. Diabetes will include the preferred terms of ‘Diabetes mellitus’, ‘Type 1 diabetes mellitus’, or ‘Type 2 diabetes mellitus’. Diabetes will not include subjects who report ‘Glucose tolerance impaired’ (borderline diabetes or pre-diabetes), ‘Diabetic vascular disorder’ or ‘Blood glucose increased’. All medical history terms will be reviewed by the study medical monitor to determine if any other terms should be included in the summary.

Age at EFP symptoms onset will be computed as the date of the EFP symptoms reported on the medical history page minus the date of birth divided by 365.25. If the date of EFP symptom onset is incomplete, the date will be imputed according to the rules set up in section 3.5.3.

3.2.6.5. Prior and Concomitant Medications

All medications will be coded with the WHO drug dictionary, Version 01 MAR2016. A concomitant medication is any medication with a stop date on or after the date of the first injection or the medication is reported as ongoing. A prior medication is any medication with a start date prior to the date of the first injection.

3.2.6.6. Prior EFP Treatment

Prior EFP treatment will be obtained from the prior/concomitant medication and prior/concomitant procedure pages of the electronic Case Report Form (eCRF). If on either of these pages a medication or treatment is reported with the indication 'EFP/Cellulite' with a start date prior to the first dose of study medication, then the medication or procedure will be considered a prior EFP treatment. All medications will be classified as EFP Drug. All procedures will be classified into one of the following groups:

- Liposuction
- Laser
- Massage
- Radiofrequency
- Mesotherapy
- Cream
- Other

The classification will be reviewed and approved by the study medical monitor. Any EFP treatment used after the Day 1 visit will be noted and reported as a protocol violation.

Time since the last EFP treatment will be computed as the date of the most recent EFP treatment minus the date the informed consent was signed divided by 365.25. If the date of any EFP treatments is incomplete, the date will be imputed according to the rules set up in section 3.5.3.

3.3. ANALYSIS POPULATIONS

The following populations are considered in the statistical analysis of the study: safety population and effectiveness population.

3.3.1. Safety Population

The safety population is defined as all enrolled subjects who have at least one injection of study medication. All safety parameters will be summarized based on this population.

3.3.2. Effectiveness Population

The effectiveness population is defined as all subjects in safety population with a baseline and at least 1 post-injection evaluation of the Investigator CR-PCSS in at least one treatment area.

All evaluations of effectiveness will be based on the effectiveness population.

3.4. STATISTICAL METHODS

3.4.1. General Consideration

In general, descriptive statistics for continuous variables may include number of subjects (n), mean, standard deviation, median, minimum and maximum values. Analysis of categorical variables will include frequency and percentage.

3.4.2. Subject Disposition

The total number of patients will be summarized for the following categories: those who were screened and those who screen failed.

The number and percentage of patients within each assigned region (buttock or thigh) and overall treatment group will be presented by the following categories: enrolled, completed the study, discontinued from the study (and reasons), and those who are included in safety population, effectiveness population, and photographic sub-study. The percentages are based on the number of the subjects who were enrolled into the study.

The descriptive statistics of time in the study (days) including number of subjects (n), mean, standard deviation, median, minimum and maximum values will also be provided.

The number and percentage of subjects by investigational site will also be summarized by assigned region (buttock or thigh) and overall treatment group.

Listing of all discontinued subjects and listing of subjects excluded from analysis populations will be generated.

3.4.3. Demographics and Baseline Characteristics

Demographics and baseline characteristics will be summarized by assigned region (buttock or thigh) and overall for safety population, and will include:

- Age
- Age category (≥ 18 to < 35 years, ≥ 35 to < 45 years, ≥ 45 to < 55 years, ≥ 55 to < 65 years, ≥ 65 years)

- Gender
- Race
- Ethnicity
- Weight (in kg)
- Height (in cm)
- BMI (in kg/m²)
- BMI group (underweight [< 18.5 kg/m²], normal weight [≥ 18.5 to < 25.0 kg/m²], overweight [≥ 25.0 to < 30.0 kg/m²], obese [≥ 30.0 kg/m²])
- Skin category based on Fitzpatrick scale rating
- Alcohol use
- Tobacco use

Individual subject listing of all demographic and baseline characteristics will be generated.

3.4.4. EFP Risk Factors and EFP History

EFP risk factors and EFP history characteristics will be summarized by assigned region (buttock or thigh) and overall for both the safety population and effectiveness population, and will include:

- Family history of cellulite
- Medical history of Dupuytren's disease, knuckle pads, Ledderhose's disease, diabetes, epilepsy (see [section 3.2.6.4](#))
- Age at EFP symptom onset (in years)
- Prior treatments for EFP including Liposuction, Laser, Massage, Radiofrequency, Drug, Mesotherapy, Cream, Other or None. Subjects can report more than one prior EFP treatment.
- Number of prior EFP treatments (0, 1, 2, or ≥ 3)
- Time since most recent EFP treatment (in years)

3.4.5. EFP Baseline Severity

EFP baseline severity variable characteristics (including CR-PCSS rating and Hexsel CSS total score from Screening Visit) will be summarized by assigned region (buttock or thigh) and overall in the safety population.

Individual subject listing of all Hexsel CSS results will be generated.

3.4.6. Effectiveness Evaluation

All analyses for effectiveness evaluation will be conducted in the effectiveness population.

3.4.6.1. CR-PCSS

3.4.6.1.1. CR-PCSS Rating Summaries

The investigator CR-PCSS ratings will be summarized by assigned region (buttock or thigh) and overall at baseline (prior to Day 1), Day 22, Day 43, Day 90, and Day 180 (EOS/ET) with counts and percentages at each severity rating and with means and standard deviation. The change from baseline in CR-PCSS score will be summarized by assigned region (buttock or thigh) and overall at Day 22, Day 43, Day 90, and Day 180 (EOS/ET) with counts at each change score and with means and standard deviation. The change from baseline score can vary from -4 (change from severe to none) to +2 (change from mild to severe).

Individual subject listing of CR-PCSS ratings will be generated.

3.4.6.1.2. Responder Summaries

The investigator CR-PCSS responder classification will be summarized by assigned region (buttock or thigh) and overall (buttock and thigh) at Day 22, Day 43, Day 90, Day 180 (EOS/ET) with counts and percentages for both two-level responders and the one-level responders.

3.4.6.2. Subject Satisfaction with Cellulite Treatment Assessment

Subject satisfaction with cellulite treatment will be summarized by assigned region (buttock or thigh) and overall with counts and percentages for each response level. Additionally the mean and standard deviation of responses within each assigned region and overall will be presented. Subject satisfaction scores include +2 (Very Satisfied), +1 (Satisfied), 0 (Neither Dissatisfied nor Satisfied), -1 (Dissatisfied), and -2 (Very Dissatisfied).

Individual subject listing of subject satisfaction with cellulite treatment will be generated.

3.4.7. Safety Analysis

All analyses for safety will be conducted in the safety population.

3.4.7.1. Adverse Events

The following listings will be provided based on all AEs:

- Listing of AEs
- Listing of deaths
- Listing of SAEs
- Listing of AEs leading to discontinuation

The following summary tables of AEs will be presented by assigned region (buttock or thigh) and overall:

- Treatment-Emergent AEs
 - Overall summary
 - By preferred term

- By preferred term and severity
- By frequency for SAEs
- By frequency for most common non-serious AEs
- Treatment-Related AEs
 - Overall summary
 - By preferred term
 - By preferred term and severity
 - By preferred term and treatment session
 - Duration of AEs

The overall summary will consist of the following items:

- Total number of AEs
 - All AEs
 - Mild AEs
 - Moderate AEs
 - Severe AEs
- Total number of subjects with
 - At least one AE
 - At least one SAE
 - At least one severe AE
 - At least one AE leading to discontinuation
- Total number of subjects who died (Treatment-emergent only)

Percentages for the total number of mild, moderate, and severe AEs will be based on the total number of all AEs in the corresponding assigned region and overall.

The by frequency summaries will also include the total number of occurrences the AE preferred term was reported as well the number of subjects with at least one report of the AE. Most common non-serious AEs are any preferred term AE that at least 5% of the subjects report at least once.

3.4.7.1.1. Adverse Event Conventions

The following conventions will be followed:

- Table by preferred term - If an AE preferred term occurred multiple times within a body system for the same subject, the preferred term will only be counted once for the subject for the summary of preferred terms. If an AE body system occurred multiple times for the same subject, the body system will only be counted once for the subject

for the summary of body systems. If a subject has any AE, the subject will be counted once in the summary of subjects with at least one AE.

- Table by preferred term and severity - If an AE preferred term occurred multiple times within a body system for the same subject, only the most severe one will be used. If the most severe preferred term of an AE occurred multiple times within a body system for the same subject, only one will be counted. In addition, this summary will also contain the total number of subjects with at least one mild, one moderate, or one severe. If a subject has at least one severe AE, then the subject will be counted in the severe category. If the subject has no severe AEs, but at least one moderate AE, then the subject will be counted in the moderate category, and if the subject has no severe and no moderate AEs, but has at least one mild AE, then the subject will be counted in the mild category.
- Table by preferred term and treatment session – If an AE preferred term occurred multiple times with a body system for the same subject within a treatment session, the preferred term will only be counted once for the subject in the treatment session for the summary of preferred terms. If an AE preferred term occurred multiple times within a body system for the same subject in different treatment sessions, the preferred term will be counted at each treatment session. If an AE body system occurred multiple times for the same subject within a treatment session, the body system will only be counted once for the subject in the treatment session for the summary of body systems. If an AE body system occurred multiple times for the same subject in different treatment sessions, the body system will be counted at each treatment session for the summary of body systems. If a subject has any AE within a treatment session, the subject will be counted once in the treatment session in the summary of subjects with at least one AE. If a subject has any AE in different treatment sessions, the subject will be counted in each treatment session in the summary of subjects with at least one AE.
- Table by duration of treated-related TEAE and treatment session – For each subject within each treatment session, every event will have its duration calculated. The multiple events for the same SOC and the same PT will be combined together for the sum of duration. Therefore for each SOC/PT in each treatment session, each subject will only have at most one (sum) duration which will be classified into one of the duration categories (≥ 1 to ≤ 4 days, > 4 to ≤ 7 days, > 7 to ≤ 14 days, ≥ 15 to ≤ 21 days, and >21 days).
- For ongoing AEs, the category of AE duration will be missing unless those events have an onset date 21 days prior to the subject's last visit in the study. In this case, the category of the AE duration will be classified as " > 21 days".
- Table of frequency of preferred terms – Preferred terms will be ordered by their descending frequency in the overall safety population. If 2 or more preferred terms are tied in their frequency, then the preferred terms will be ordered alphabetically.

